### **8.8.3 Immediately Reportable Events**

The investigator/subinvestigator or designee must immediately report (within 24 hours), using forms including an IRE form, after he/she or site personnel become aware of any IRE (SAE, AE related to occupational exposure, potential serious hepatotoxicity, or confirmed pregnancy), by e-mail in principle to the sponsor or designee using the contact information on the cover page of this protocol (please note that the IRE form is NOT the entry column for AEs in the eCRF). Patient confidentiality must be protected and contact information such as name, address, phone number or any other protected health information as determined by applicable local regulation must be redacted when forwarding Safety Information and supporting documentation. Details regarding the follow-up of IREs are included in [Section 8.8.8.2](#).

### **8.8.4 Medical Device Incidents (Including Malfunctions)**

Not applicable.

### **8.8.5 Adverse Events of Special Interest**

Not applicable.

### **8.8.6 Potential Serious Hepatotoxicity**

For a subject who experiences an elevation in AST or ALT that is  $\geq 3$  times the ULN, a total bilirubin level should also be evaluated. If the total bilirubin is  $\geq 2$  times the ULN, complete an IRE form or other documentation with all values listed and also report as an AE in the eCRF.

### **8.8.7 Procedure for Breaking the Blind**

This trial does not use blinding procedures.

## **8.8.8 Follow-up of Adverse Events**

### **8.8.8.1 Follow-up of Nonserious Adverse Events**

Nonserious AEs that are identified at any time during the trial must be recorded on the AE eCRF with the current status (ongoing or resolved/recovered) noted. All nonserious events (that are not IREs) that are ongoing at the last scheduled contact will be recorded as ongoing in the eCRF. For any AE having been identified throughout the trial, during analysis, additional relevant medical history information may be requested by the sponsor to further ascertain causality (including, but not limited to, information such as risk-related behavior, family history, and occupation).

### **8.8.8.2 Follow-up of Immediately Reportable Events**

This trial requires that subjects be actively monitored for IREs up to the last scheduled contact (Week 56, 28 days after the last dose of IMP is administered).

Immediately reportable events that are identified or ongoing at the last scheduled contact must be recorded as such on the AE eCRF page and the IRE form or other documentation. If updated information (eg, resolved status) on IRE status becomes available after a subject's last scheduled contact (up to last in-clinic visit for the entire trial), this must be reported to the sponsor and recorded on the AE eCRF page and the IRE form or other documentation, according to the appropriate reporting procedures described in [Section 8.8.3](#).

It is expected that the investigator or subinvestigator will provide or arrange appropriate supportive care for the subject and will provide prompt updates on the subject's status to the sponsor. The investigator or subinvestigator will follow IREs until:

- The events have resolved,
- The events have stabilized,
- The subject is lost to follow-up, or
- The subject has died.

Resolution means that the subject has returned to the baseline state of health and stabilized means that the investigator or subinvestigator does not expect any further improvement or worsening of the subject's condition. The investigator or subinvestigator will continue to report any significant follow-up information to the sponsor up to the point the event has resolved or stabilized, or the subject is lost to follow-up, or has died.

Refer to [Section 10.3](#) for additional information regarding the duration of follow-up for subjects that become pregnant or for pregnant partners of male subjects.

#### **8.8.8.3 Follow-up and Reporting of Immediately Reportable Events Occurring After Last Scheduled Contact**

Any new IREs reported to the investigator or subinvestigator which occur after the last scheduled contact and are determined by the investigator or subinvestigator to be reasonably associated with the use of the trial intervention, should be reported to the sponsor according to the procedures outlined in [Section 8.8.3](#). This may include IREs that are captured on follow-up telephone contact or at any other time point after the defined trial period and continue to report any significant follow-up information to the sponsor until the events are resolved or stabilized, or the subject is lost to follow-up or has died.

### **8.9 Treatment of Overdose**

For treatment of overdose, refer to the overdose section of the IB. There is no specific treatment for overdose with ETC-1002. In the event of overdose, symptomatic and supportive therapies should be provided as appropriate.

### **8.10 Subject Assessment Recording**

#### **8.10.1 Completion of the Subject Diary**

The investigator or subinvestigator will instruct the subjects who are judged able to receive the IMP to enter the status of compliance with the IMP and lipid-lowering drugs in the subject diary, and bring it to the visit. The investigator or subinvestigator will record the status of compliance with the IMP and lipid-lowering drugs in the eCRF based on the contents entered in the subject diary.

### **8.11 Other Assessments**

#### **8.11.1 Pregnancy Test**

A urine test will be performed for females of childbearing potential according to the schedule specified in Table 1.3-1, and the date and result of the test will be recorded in the source document and the eCRF. A definition of childbearing potential can be found in [Section 10.3](#). Subjects with a positive urine test will be withdrawn from the trial.

However, any positive urine test on or after Day 1 will lead to a re-test using serum to confirm the diagnosis, and the date of blood sampling will be recorded in the source document and the eCRF. If the serum test is positive, the investigator or subinvestigator will report it to the sponsor as an IRE.

The serum test will be performed by the central laboratory selected by the sponsor. Proper sample collection, handling, and shipping procedures will be provided to the trial sites in a separate manual prior to the start of the trial. The central laboratory will report the test results to the investigator or subinvestigator who confirms the test results. The laboratory report will be officially documented by entering the date of confirmation and signing the report by the investigator or subinvestigator. The results of the serum test will be directly reported to the sponsor by the central laboratory in electronic files. Therefore, it is not necessary to record the results in the source document and the eCRF.

### **8.11.2 Endocrine Test and Virus Test**

Samples for the endocrine test (of TSH) and the virus test (of HBsAg and HCV antibodies) will be collected at Week -2 in newly enrolled subjects to confirm eligibility of subjects regarding thyroid and liver function. The date of blood sampling will be recorded in the source document and the eCRF. Samples will be shipped to the central laboratory selected by the sponsor, and eligibility will be confirmed based on the test results measured by the central laboratory. Proper sample collection, handling, and shipping procedures will be provided to the trial sites in a separate manual prior to the start of the trial. The central laboratory will report the test results to the investigator or subinvestigator who confirms the results. The laboratory report will be officially documented by entering the date of confirmation and signing the report by the investigator or subinvestigator. The test results will be directly reported to the sponsor by the central laboratory in electronic files. Therefore, it is not necessary to record the results in the source document and the eCRF. Since the eligibility of the rollover subjects has been confirmed in the phase 3 confirmatory trial (Protocol No. 346-102-00002), it is not necessary to conduct the test in this trial.

## **9 Statistical Considerations**

### **9.1 Sample Size**

Assuming a withdrawal of approximately 20 subjects during the treatment period, the target number of subjects is set at 120 to ensure that 100 subjects will complete the 1-year treatment to assess the safety of ETC-1002 at 180 mg in long-term administration.

### **9.2 Datasets for Analysis**

The safety analysis set will include subjects who receive at least one dose of the IMP during the treatment period.

The efficacy analysis set will include subjects who receive at least one dose of the IMP during the treatment period, and who have LDL-C measurements at baseline and at one or more time points after administration of the IMP during the treatment period.

### **9.3 Handling of Missing Data for Primary Endpoint Analysis**

Missing data will not be imputed.

### **9.4 Statistical Analyses**

#### **9.4.1 Efficacy Analyses**

Efficacy analyses will be performed using the efficacy analysis set by rollover subjects, newly enrolled subjects, and overall (rollover and newly enrolled) subjects. Baseline is defined as the last data before the start of IMP administration in the treatment period.

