## 1.2 Schema

Screening Period (2 weeks)	Treatment Period (52 weeks, Open-label)	Follow-up Period (4 weeks)
-------------------------------	--	-------------------------------

[Rollover subjects from Trial 346-102-00002 will proceed directly to the treatment period of this trial (52 weeks, open-label) after completing the 12-week double-blind treatment period.]

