**Figure 1.2-1 Trial Design Schematic**

### 1.3 Schedule of Assessments

	Screening Period		Treatment Period														Follow-up Period (28 days after the final IMP administration)
	Rollover Subjects	Newly Enrolled Subjects															
Visit (Week)	-4 a	-2	0 b	4	8	12	16	20	24	28	32	36	40	44	48	52/ Discontinuation c	56
Trial Day	-28 ± 3	-14 ± 7	1	29 ± 7	57 ± 7	85 ± 7	113 ± 7	141 ± 7	169 ± 7	197 ± 7	225 ± 7	253 ± 7	281 ± 7	309 ± 7	337 ± 7	365 ± 7	393 ± 7
Informed consent d	●	●															
Eligibility assessment	●	●	●														
Demographics		●															
Physical examination	●	●	●	●	●	●	●	●	●	●	●	●	●	●	●	●	●
Body weight		●	●	●		●		●	●	●		●		●		●	●
Endocrine test (TSH), virus test (HBsAg, HCV antibody)		●															
Vital signs e	●	●	●	●	●	●	●	●	●	●	●	●	●	●	●	●	●
12-Lead ECG f		●	●			●			●			●				●	
Clinical laboratory tests g	●	●	●	●	●	●	●	●	●	●	●	●	●	●	●	●	●
Fasting lipids h, i	●	●	●	●	●	●	●	●	●	●	●	●	●	●	●	●	
HbA1c i		●	●			●			●			●				●	
hsCRP, apo B l			●			●			●			●				●	
Confirmation of use of concomitant medications/therapies	←																→
Adverse events	←																→
Pregnancy test j		●	●			●			●			●				●	
Blood sampling for DNA storage k			○														
Dispensing of IMP			●	●	●	●	●	●	●	●	●	●	●	●	●		
Provision of subject diary			●	●	●	●	●	●	●	●	●	●	●	●	●		
Collection of unused IMP and subject diary				●	●	●	●	●	●	●	●	●	●	●	●	●	

● Mandatory; ○ Optional

- aThe results of the scheduled tests performed at Week 8 in the phase 3 confirmatory trial (Protocol No. 346-102-00002) will be used.
- bBody weight and 12-lead ECG will not be required on Day 1 if they have been performed within 7 days prior to Day 1 in the screening period. The results of the scheduled tests performed at Week 12 in the phase 3 confirmatory trial (Protocol No. 346-102-00002) will be used for rollover subjects.
- cIn cases of early discontinuation during the treatment period, the same assessments as in Week 52 are to be performed at Discontinuation Visit within 2 days after the last dose of the IMP as far as possible.

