### **5 Trial Population**

This trial will include Japanese patients with hyper-LDL cholesterolemia aged 18 years or older at the time of informed consent and with an inadequate response to statins or difficulty in treatment with statins, who cannot achieve the lipid management goals specified in the Japan Atherosclerosis Society Guidelines for Prevention of Atherosclerotic Cardiovascular Diseases 2017. Subjects who are determined to be eligible by the investigator or subinvestigator in the screening period will proceed to the treatment period. The subjects who have completed the treatment period in the phase 3 confirmatory trial (Protocol No. 346-102-00002) can also be enrolled in this trial, as they are in the same population. Such subjects who are determined to be eligible based on the results of the scheduled tests at Week 8, after obtaining written informed consent for participation in this trial following Week 8, will proceed to the treatment period of this trial and start receiving the IMP, ETC-1002 at 180 mg for this trial, after completion of the Week 12 assessments. The number of subjects starting the treatment is set at 120 to ensure that at least 100 patients will complete the treatment at Week 52. The number of patients who have difficulty in treatment with statins is planned to be at least 20% among the entire number in this trial.

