3.4 Trial Visit Window

For the efficacy and safety endpoints (except for AEs), acceptable windows of analysis visits will be set, and the analysis will be based on the analysis visits, regardless of the time points recorded in the case report form (CRF). Analysis visits will be specified based solely on fasting data for non-HDL-C, TC, HDL-C, TG, and LDL-C (calculated using the Friedewald formula) among the fasting lipid parameters for the efficacy endpoints. The handling of fasting data is described in [Section 5.3](#).

Acceptable windows of analysis visits are shown in [Table 3.4-1](#). The start day of investigational medicinal product (IMP) administration is defined as Day 1. Baseline is defined as the last data before the start of IMP administration. If multiple data points are available for a certain acceptable window, the last data point will be used for the analysis. Data collected more than 2 days after the last IMP administration will be excluded. The last data obtained between the initial IMP administration and 2 days after the last IMP administration will be defined as the Last Visit.

Table 3.4-1 Acceptable Windows of Analysis Visits	
Week	Trial Day Interval
Baseline	- 1
Week 4	2 - 43
Week 8	44 - 71
Week 12	72 - 99
Week 16	100 - 127
Week 20	128 - 155
Week 24	156 - 183
Week 28	184 - 211
Week 32	212 - 239
Week 36	240 - 267
Week 40	268 - 295
Week 44	296 - 323
Week 48	324 - 351
Week 52	352 - 375
Last Visit	Last data obtained between the initial IMP administration and 2 days after the last IMP administration in the treatment period
Week 56 (FU)	Time point recorded in the CRF

4 Sample Size

Assuming a withdrawal of approximately 20 subjects during the treatment period, the target number of subjects is set at 120 to ensure that 100 subjects will complete the 1-year treatment to assess the safety of ETC-1002 at 180 mg in long-term administration.

5 Statistical Analysis Datasets

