7.6 Protocol Deviations

For subjects with IMP administration, frequency distributions of the presence/absence of the following categorized deviations recorded in the CRF will be summarized by rollover, newly enrolled, and overall subjects.

- Dosing
- Inclusion/exclusion criteria
- Met withdrawal criteria but was not withdrawn
- Procedural deviations (affecting primary outcome variables)
- Prohibited concomitant medications

The same analysis will be performed for each statin response (inadequate response to statins/difficulties in treatment with statins).

8 Efficacy Analysis

Efficacy analyses will be performed using the efficacy analysis set, by rollover subjects, newly enrolled subjects, and overall (rollover and newly enrolled) subjects. The analysis visits will be Weeks 4, 8, 12, 16, 20, 24, 28, 32, 36, 40, 44, 48, and 52, unless otherwise specified.

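### Rollover subjects who took ETC-1002 in the confirmatory trial enter with an on-drug baseline, so the rollover and overall percent-change columns mix maintenance with onset of effect and are pulled toward zero

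*Protocol*

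**What the plan says.** Protocol 9.4.1 defines the efficacy baseline: "Baseline is defined as the last data before the start of IMP administration in the treatment period". Protocol 9.4.2 repeats this for safety. SAP 3.4 has the same rule, "Baseline is defined as the last data before the start of IMP administration", and fixes the clock with "The start day of investigational medicinal product (IMP) administration is defined as Day 1". Neither document has a separate baseline rule for rollover subjects.

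The Day 1 data of rollover subjects come from the earlier trial. Footnote b to the schedule in Protocol 1.3 takes them from "The results of the scheduled tests performed at Week 12 in the phase 3 confirmatory trial". The schema in Protocol 1.2 says that these subjects "will proceed directly to the treatment period of this trial (52 weeks, open-label) after completing the 12-week double-blind treatment period", and Protocol 5 says that they "start receiving the IMP, ETC-1002 at 180 mg for this trial, after completion of the Week 12 assessments".

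On presentation, SAP 8 says: "Efficacy analyses will be performed using the efficacy analysis set, by rollover subjects, newly enrolled subjects, and overall (rollover and newly enrolled) subjects". SAP 8.1 repeats the analyses by statin response. The subgroup list in SAP 8.3 and the tables in SAP Appendix 8 contain no split by treatment received in the confirmatory trial. No output uses that trial's pre-dose value, and SAP 14 records no change to the planned analyses.

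**The concern.** The first efficacy endpoint in Protocol 3 is percent change in LDL-C from baseline to Week 52, which serves the secondary objective on the effect of 52 weeks of ETC-1002. For a subject already treated for 12 weeks, Day 1 LDL-C has already fallen. If the drug goes on working fully, that subject's change to Week 52 is about zero.

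Averaging such subjects with others who start from an untreated value gives a figure that depends on how many previously treated rollovers enrolled as well as on the drug. A reader could take a modest rollover or overall figure for a weak or fading effect. The rollover column alone can show neither onset nor maintenance.

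The same rule governs the other percent-change endpoints and the change-from-baseline laboratory tables. Protocol 2.3 reports that, in trials outside Japan, mean uric acid rose within the first month and then stayed stable. Previously treated rollovers would therefore be expected to show little further rise, which would understate a known signal in the pooled columns.

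**Working it through.** **The plan's own figure.** The only sample-size figure is 120 treated subjects for 100 completers, allowing about 20 withdrawals (Protocol 9.1; SAP 4): 100 + 20 = 120, which reproduces. No effect size, power or precision target is set for LDL-C.

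**Inputs**
- E, the Week 52 percent change from an off-drug baseline. I take -21.26%, the phase 2 Week 12 mean on 180 mg (Protocol 2.1). Placebo was -1.92%, so the difference is -21.26 + 1.92 = -19.34 points.
- f, the share of rollovers who had prior ETC-1002. Not stated; assumed 1/3, 1/2 or 2/3.
- r, the share of all subjects who are rollovers. Not stated; assumed 25%, 50% or 75%.

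**Formulas.** With a stable effect, previously treated rollovers change by 0 and all others by E. Hence:
- rollover column = (1 - f) × E
- overall column = (1 - r × f) × E

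**Results with E = -21.26%**

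| f | Rollover column | Overall, r = 25% | Overall, r = 50% | Overall, r = 75% |
|---|---|---|---|---|
| 1/3 | -14.2% | -19.5% | -17.7% | -15.9% |
| 1/2 | -10.6% | -18.6% | -15.9% | -13.3% |
| 2/3 | -7.1% | -17.7% | -14.2% | -10.6% |

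Example: -21.26 × (1 - 0.5 × 0.5) = -15.9%.

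**Sensitivity, f = 1/2**
- Placebo-adjusted E: rollover column -19.34 × 0.5 = -9.7%.
- E by statin response at 180 mg (Protocol 2.1): inadequate response, -16.31 × 0.5 = -8.2%; statin intolerance, -31.25 × 0.5 = -15.6%.
- 80% of the effect left at Week 52: off-drug starters show 0.8 × -21.26 = -17.0%. Previously treated subjects show (100 - 17.008)/(100 - 21.26) - 1 = +5.4%. The rollover mean is -5.8%, against -17.0% undiluted.
- Effect grown to 120%: off-drug starters show -25.5% and previously treated subjects -5.4%. The rollover mean is -15.5%, against -25.5% undiluted.
- A further 10% reduction in everyone from lipid-lowering therapy added after Week 12: previously treated subjects show -10.0% and the others 0.7874 × 0.9 - 1 = -29.1%. The rollover mean is -19.6%, against -29.1% undiluted.

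In every case the rollover mean lies closer to zero than the change in subjects with an off-drug baseline.

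**The case against.** The strongest reply is that this is an uncontrolled, descriptive trial with safety as its primary objective. SAP 6 names no primary or secondary outcome variables, and Protocol 4.1 admits rollovers so that adverse events can be followed for longer. No test, alpha or power is affected. Every efficacy analysis is also shown for newly enrolled subjects alone, and exclusion criterion 18 keeps previous ETC-1002 users out of that group, so its baseline is off-drug. Actual LDL-C values are reported too. All of this stands. It limits the harm to the change and percent-change results in the rollover and overall columns, but it does not make those columns interpretable.

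It is also fair that the documents do not state the confirmatory trial's arms, comparator or allocation. That some rollovers had ETC-1002 is a well-supported inference. The trial was double-blind and designed from the dose-finding results (Protocol 2.2), the rollover exclusion list has no prior-use criterion, and Protocol 8.1 withholds blinded results at rollover Week -4 and Day 1. That the others had placebo is also an inference, and the mix is unknown. Lipid-lowering therapy may be added from Week 12 (Protocol 6.1), so a previously treated subject need not show exactly zero. The direction survives; the figures are not predictions.

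Three stronger readings might be inferred, and the documents do not support them:
- *Goal attainment at Week 52 is diluted.* It is the proportion below the goal at that visit and uses no baseline.
- *The baseline LDL-C class below 100 mg/dL will consist largely of previous responders.* Rollovers have no LDL-C entry criterion, so some may fall there. But the 100 mg/dL floor for new subjects applies at screening, and they can drop below it by Day 1. Nothing supports a majority claim.
- *The overall column should be re-based on the value before the first ETC-1002 dose.* That would pool 12 + 52 = 64 weeks of exposure with 52 weeks and depart from the baseline in Protocol 9.4.1.

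**Conclusion.** The point holds for the rollover and overall change and percent-change columns. Any share of previously treated rollovers above zero moves the pooled LDL-C change toward zero if the drug effect persists. Under the assumed shares (f from 1/3 to 2/3, r from 25% to 75%), with a stable effect equal to the phase 2 mean, the rollover column would read -14.2% to -7.1% and the overall column -19.5% to -10.6%, in place of -21.26%. The actual size cannot be fixed from the documents.

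This is a gap in stratification and labelling that affects how a secondary endpoint is read. It does not show that the trial cannot estimate the 52-week effect: the newly enrolled column does so now, and rollovers without prior ETC-1002 would add to it once separated.

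**What to change.** 1. In SAP 8.1 to 8.3 and the matching Appendix 8 tables and figures, split the rollover column by treatment received in the confirmatory trial, using the allocation after unblinding (Protocol 8.1 anticipates unblinding).
2. Keep the Day 1 baseline, but label the change in prior ETC-1002 rollovers as maintenance of effect.
3. State that the pooled rollover and overall percent changes are not the 52-week effect. Take that from newly enrolled subjects plus rollovers without prior ETC-1002.
4. As a supplementary table, show prior ETC-1002 rollovers against the confirmatory trial's pre-dose baseline, labelled as about 64 weeks of exposure. This depends on obtaining that value: the documents describe use of Week 8 and Week 12 results only.
5. Apply the same split to the other lipid markers, hsCRP, HbA1c and the laboratory change-from-baseline tables in SAP 9.3, and record the change in SAP 14.

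The cost is a data merge and extra tables with smaller groups. No new visits or subjects are needed.
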